### 6.2. Interventionist Training, Tracking and Fidelity

To ensure fidelity of the intervention we have outlined a detailed training program and fidelity checklist. In Figure 1 we outline our training timeline. In year 1, [name] will adapt the training content from our COVID-19 'Motivate, Vaccinate, Activate' intervention for RSV vaccination. The training materials will be reviewed by our community-academic core team and refined with CHWs during the production phase of Aim 1. In year 2, we will train CHWs to deliver the intervention and assess competency with written assessments and direct observation at the end of training. We will score competency with a fidelity checklist that includes fidelity to the intervention, accuracy of content, and participant satisfaction. Throughout the trial there will be direct observation to ensure fidelity to the CHW counseling sessions (first 5 participants and quarterly) and we will hold monthly CHW meetings to reinforce skills and address questions. This plan is guided by the NIH Behavior Change Consortium recommendations to ensure fidelity of treatment delivery through standardized training, ensuring provider skill acquisition, minimizing drift (with observation and feedback), and accommodating provider differences (tailoring intervention to CHWs).

**Details on measuring the fidelity counseling intervention in Aims 2 & 3.** We will measure four dimensions of fidelity: (1) **adherence** (delivery as designed) through fidelity checklists—direct observation and CHW fidelity-checklists (2) **dosage** (amount of intervention delivered) time and content measured through a CHW fidelity checklist, (3) **quality**, through participant post-intervention rating and an empathy question on the fidelity checklist (4) **program differentiation**, through fidelity checklist in the intervention and control (Table 2). The primary fidelity measure will be percent of activities completed on the fidelity checklist, measured by direct observation. In developing the fidelity checklists, we will follow the process outlined by Walton et al. 2020^59 and will assess adherence to each of the 5As. For example, for 'Assess', observers will choose 'Done', 'To Some Extent', 'Not Done' after observing if the CHW assessed participants' beliefs and knowledge about RSV susceptibility. Additionally, we will

assess quality of delivery using the validated empathy question from the Motivational Treatment Integrity Scale.

### **6.3. Participant Discontinuation/Withdrawal from the Study**

Participants are free to withdraw from participation in the study at any time upon request.

An investigator may discontinue a participant from the study for the following reasons:

- Unacceptable adverse event(s)
- Significant study intervention non-compliance.
- Lost-to-follow up; unable to contact participant (see Section 6.4 - Lost to Follow-Up)
- Any event or medical condition or situation occurs such that continued collection of follow-up study data would not be in the best interest of the participant .
- The participant meets an exclusion criterion (either newly developed or not previously recognized) that precludes further study participation

### **6.4. Lost to Follow-up**

A participant will be considered lost to follow-up if he or she fails to return for scheduled visits and study staff are unable to contact the participant after at least 3 attempts. Before a participant is deemed lost to follow-up, the investigator or designee will make every effort to regain contact with the participant (where possible, 3 telephone calls and, if necessary, a letter to the participant's last known mailing address or local equivalent methods). These contact attempts will be documented in the participant's study file. Should the participant continue to be unreachable, he or she will be considered to have withdrawn from the study with a primary reason of lost to follow-up.

## **7. Study Procedures and Assessments**

### **7.1. Informed Consent and Enrollment**

Prior to consent, participants will be screened to determine eligibility in the intervention. A waiver of consent will be obtained to confirm eligibility during the screening process. Written informed consent to participate in the study will be obtained from all participants. Consent forms will be translated from the original English to Spanish. Participants who agree to take part and sign the consent form will be enrolled in the study. Participants who can neither read nor write will have an impartial witness present during the consenting process who will sign and date the consent form on a line provided for witnesses upon confirming that the participant's consent is given voluntarily and freely. Illiterate participants may mark an X on the signature line if they cannot sign themselves and the witness will provide the date next to the participant's signature line.

#### Aim 1: Informed Consent procedures:

- Community RSV Vaccine Confidence Survey: Informed consent information sheet.
- Community Advisory Board Meetings: Electronic or written informed consent.
- In depth interview: Electronic or written informed consent.

## Study Procedures AIM 1 (Developmental Aim)

Prior to implementation of the randomized trial, we will adapt the intervention using the ADAPT-ITT process (Figure 2). Study procedures will include: a community member vaccine hesitancy survey (anonymous), observation of 3-5 community advisory groups process in adapting intervention, and qualitative interviews.

### Phase 1:

*a. Community RSV vaccine hesitancy survey:* A 25-minute survey will include demographics (age, gender, income, country of birth), BeSD core questions, prior vaccine history, self-rated health, experiences with healthcare discrimination, social network influences about health decisions, acculturation scale.

*b. In-depth Interviews (IDI):* 90-minute interviews will focus on (1) Drivers of RSV vaccine confidence to guide adaptation of CHW counseling (2) cultural tailoring and preferences for content of text message, CHW counseling and informational link in the text message, (3) Older adults' preferences and attitudes about how best younger people can discuss RSV vaccination with them ( $\geq 60$  years) and (4) Barriers and facilitators to discussing vaccines with older adults in the IDI (18-50 years). Interviews will be conducted by bilingual and bicultural staff from UCSF, trained in qualitative methods. *Based on our prior qualitative work on intervention design we anticipate adequate thematic saturation with N~40 in total for Aim 1.1 & 1.2.*

Community Advisory Board meetings (ADAPT-ITT): Over 3-5 CAB meetings, the CAB will discuss RSV vaccine hesitancy, perceptions of intervention components (text and CHW counseling) and work with the study team to adapt the intervention components. After the first iteration of the adapted intervention component they will 'theatre test' the intervention components with the study team and provide feedback to develop the final version of the intervention components for Aims 2 and 3. *The size of community advisory groups* is based on sizes used in ADAPT-ITT interventions and the language distribution mirrors the community that served by the LTF and UES. Groups are larger for 18–50-year-olds to incorporate the diversity of preferred languages and any differences in preferences among young adults (18-24 years) vs. adults 25-50 years.

## 7.2. Randomization and Interventions for Trials

### 7.2.1. Randomization and Interventions for 'Motivate' Trial (Aim 2)

This is a two-arm randomized type-1 effectiveness-implementation individually randomized trial. We will randomize individuals to one of the two study groups (see 8.2.2) with random block sizes of 2 and stratified by sex.

The two randomization groups are described in 4.3.3 and are:

**Arm 1- Text message nudge**

**Arm 2: CHW counseling and text message nudge**

### 7.2.1.1. Procedures Aim 2

**Baseline survey:** After providing informed consent, participants will complete a 30 minute baseline survey, which will include questions on demographics, knowledge of RSV and the RSV vaccine, vaccine confidence, acculturation scale. We will use the standardized vaccine hesitancy scale and BeSD vaccine hesitancy scale.

**Intervention delivery:** The schedule of interventions is outlined in Figure 6 and outlined in the Schedule of Activities in **Section 7.3**. With texts sent 4 weeks post-enrollment in both arms and the CHW counseling within 2 weeks of enrollment.

**Endpoint survey:** Participants will receive a 60-day endpoint survey with similar questions to those asked at baseline: vaccine confidence, BeSD framework core-questions, self-reported vaccination status and location, location of vaccination, self-reported number of discussions of RSV vaccination with people  $\geq 50$  years, proportion who received text message. We will also assess implementation-specific factors: (1) Process measures (e.g. text messages received, access-related challenges in getting vaccinated, called LTF hotline), location of vaccination, access-related barriers to vaccination (i.e. challenges making an appointment) and (2) Pathways: (a) whether the interventions elicited responses along the intended pathways, e.g. did the text message positively *reinforce* or remind people to take action on intended behavior, did CHW counseling improve trust and perceptions of RSV susceptibility and (b) assess subjective rating or satisfaction of interventions by participants with Likert-style questions.

[figure not shown]
**Process Metrics/CHW log:** CHW will enter the following process measures into a log that will be entered in REDcap: fidelity to counseling script, time for each motivation session, perceived client-specific barriers and facilitators, number of calls received or made for navigation and counseling.

**Text message receipt confirmation:** Text-messages will be sent 4 weeks post-enrollment. Successful receipt will be assessed retrospectively via Twilio and self-report of reading the text will be assessed at the time of the endpoint questionnaire.

**Ascertainment of vaccination status:** Vaccine status will be ascertained prior to text nudge and at 60 and 90 days through the medical record or California Immunization Registry (CAIR), the medical record, or proof of vaccination from a pharmacy.

**Semi-structured IDI with participants:** In accordance with principles of Grounded Theory, we will iteratively collect and rapidly analyze interview transcript data, continuing to select

**Figure 6: Schedule of Evaluations and Procedures**

participants within theoretically informed categories (e.g. not only categories such as study group and vaccine uptake, but levels of acculturation or baseline level of engagement with primary care). The interview guide will be designed to elicit: i) perceptions, attitudes, preferences related to the study interventions received, ii. motivations and barriers to getting RSV vaccination (per BeSD framework, Figure 3), iii. implementation outcomes: satisfaction with intervention components. Based on prior qualitative work on behavioral interventions, we anticipate adequate thematic saturation with N-10-20 in each arm.

**Focus Groups with Key Stakeholders:** We will conduct focus groups of CHWs and CBO leaders to assess barriers and facilitators of implementation, adoption, and maintenance of the intervention. We will conduct purposive sampling until we attain saturation of key themes, which we anticipate will be 2 focus groups of 6 CBO leaders within the LTF (N~12) in English and on Zoom and 2 in-person focus groups in Spanish with CHWs delivering the intervention (N~12).

## 7.2.2. Randomization and Interventions for 'Activate' Trial (Aim 3)

In a parallel structure to Aim 2 we will conduct a randomized trial of the intervention components (CHW counseling and text-message from a CBO) adapted from the Development phase (aim 1). This is a two-arm type 1 effectiveness-implementation RCT randomized at the level of the individual with the following study groups outlined in section 4.4.3:

**Study Group 1: Text message nudge**

**Study Group 2: CHW 'activation' counseling with text-message nudge**

### 7.2.2.1. Study Procedures Aim 3

**Enrollment and Randomization:** Enrollment, randomization, and intervention delivery procedures are identical to Aim 2. We will use block randomization with block sizes of 2, with stratification by sex.

**Baseline Survey:** The 25-minute questionnaire will include (1) RSV vaccine hesitancy questionnaire and demographics used in Aim 1 & 2, (2) questions on capability and confidence in recommending the vaccine, (3) Ego-centric (ego=participant) 1st degree social networks of people  $\geq 50$  years (Figure 7). Using 'name generation' techniques used widely in our prior studies, participants will be asked to list the age, gender, race/ethnicity, type of relationship, residence (district, city) and perceived RSV vaccine status of family and friends age of 50 and above. This number will be used as the denominator for the primary outcome and outcomes for each social network contact named will be assessed during the endpoint survey.

**Endpoint Survey:** Participants will complete a 60-day follow-up survey (in person preferred, but phone possible) to assess the proportion of people in their 'named' network at baseline with whom they discussed RSV vaccination. Participants will be shown the characteristics of each person (relationship, age) 'named' in their 1st degree older adult network and they will answer whether they discussed vaccination with that person, why or why not, and

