### **2.3.2. Protections Against Risk**

*Privacy:* Surveys will be conducted either by staff administering them in a private location at LTF- affiliated CBOs or if preferred over the phone. In-depth interviews will occur at Mission Language Vocational School, UCSF or remotely via the online meeting platform Zoom or phone (if preferred). Community Advisory Groups will occur at Mission Language Vocational School in a private room or over Zoom.

*Data Security:* Study staff will collect all field electronic data on password encrypted devices. Any paper data collection forms, if necessary, will be data entered into a digital form, with paper forms stored in secure, locked offices at UCSF. Data will be stored in a secure cloud or on encrypted computers. For data collected as part of the study, participants will be assigned a unique identification number, and paper or electronic documentation that includes identifiers will be minimized. All study staff will be trained on procedures for maintaining confidentiality and undergo human subjects protection training.

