**Table 1: Primary Objectives**

Primary Objective	Endpoint(s)	Time Frame
1. Aim 1 (Developmental Aim) -Community-based survey on RSV vaccine hesitancy -Community advisory group adapts intervention components. -In depth interviews	N/A	1 year
2. Aim 2 (Motivate Trial): Determine the effectiveness of CHW counseling and text-message nudges from a CBO on RSV vaccine uptake among Latino older adults.	RSV Vaccine uptake at 60 days per California Immunization Registry (CAIR) or per medical record	60 days from time of intervention
3. Aim 3 (Activate Trial): Determine the effectiveness of CHW 'activation' counseling and text-message nudges from a CBO on activating adults to discuss RSV vaccination with older adults in their social network .	Self-reported average proportion of social network contacts $\geq 50$ years with whom participant discussed RSV vaccination at 60 days.	60 days from time of intervention

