#### **4.4.3. Study Design Aim 3 and Intervention Groups**

This is a two-arm type 1 effectiveness-implementation RCT randomized at the level of the individual (Figure 5) with the following **study groups**:

**Arm 1: Text message from a CBO:** Participants will receive an educational flyer from a CHW about RSV vaccination and how people in their network can schedule vaccines and the 'LTF hotline' for help with navigation if needed. Then 4 weeks later receive a text-message nudge, with message content based on findings in Aim 1b. As in Aim 2, the text message will also provide a flyer with vaccine information, eligibility, and scheduling from the LTF.

**Arm 2: CHW 'activation' counseling with text-message nudge:** At enrollment participants will receive the same flyer as in Group 1. Then, within 2 weeks of enrollment participants will have a 20-minute scripted conversation (in person or phone) grounded in motivational interviewing principals of Five A's. CHWs will assess participants beliefs and knowledge about RSV and vaccine effectiveness, safety, eligibility, *and* interest and barriers in recommending RSV vaccination to their friends or family. Then they will advise how to initiate conversations about RSV vaccination. CHWs will then assist, by assessing personal barriers to discussing vaccination with older adults. Then arrange next steps: CHWs will write down an action plan and give it to the participant. CHWs will also provide a hotline number for participants or their contacts to use for questions or support scheduling an appointment. Participants will receive a text-message nudge with scheduling and information 1 month after enrollment.

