**Questions**

Did you discuss RSV vaccine with them or their surrogate?  yes  no

If no, do you plan to discuss RSV vaccination with them in the next 3 months?  yes  no  maybe

If yes, what was the outcome of the discussion?  they already got the RSV vaccine  they scheduled an appointment  I gave them the scheduling link ..... (cont.)

the outcome of the conversation. See Figure 7 for an example of survey questions.

Implementation barriers and facilitators will be assessed as in Aim 2, with a specific focus on whether the interventions elicited responses along the intended pathways and assess subjective rating or satisfaction of interventions by participants with Likert-style questions. The endpoint survey will also include questions about vaccine confidence and specifically assess changes in trust with the BeSD core question “How much do you trust the RSV vaccine?”.

Process Metrics/CHW log: Same process measures and data collection method as described in Aim 2.

Semi-structured IDI (participants) and key stakeholders: will be assessed: We will recruit a purposive sample from each study group who completed the study procedures to understand the mechanisms by which the interventions failed or succeeded and the characteristics of who did not respond to interventions. We will use the same procedures for IDIs as discussed in Aim 2 and anticipate a sample size of N~15-25 per study group.

Focus Groups with Key stakeholders: Methods are described in Aim 2 and we will use the same focus groups with key stakeholders to assess implementation barriers for both Aims 2 and Aim 3 during the end of year 4 and quarter 1 of year 5.

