### **9.3.2. Randomization and Blinding**

Randomization for Aim 2 and 3 are referenced in section 6.1. The study statistician will be blinded to treatment arm.

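### The Activate primary outcome is live-collected self-report of the behavior Arm 2 is coached in, with no stated masking of the collector, so differential over-reporting could bias the contrast toward Arm 2

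*Protocol*

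**What the plan says.** Table 1 (section 3.1) defines the Aim 3 primary endpoint as "Self-reported average proportion of social network contacts" aged 50 or over with whom RSV vaccination was discussed by 60 days. No second source is named, and section 2.1 says that contact names are not collected. The Motivate primary outcome, by contrast, comes from the immunization registry or the medical record, and self-reported uptake is only secondary (section 3.2).

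On collection, section 7.2.2.1 states: "Participants will complete a 60-day follow-up survey (in person preferred, but phone possible) to assess the proportion of people in their 'named' network". Section 4.4.4 adds Zoom as a remote option. The general statement in section 2.3.2 is: "Surveys will be conducted either by staff administering them in a private location at LTF- affiliated CBOs or if preferred over the phone".

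On the arms, section 4.4.3 says of the counselors in Arm 2: "Then they will advise how to initiate conversations about RSV vaccination". It continues: "CHWs will write down an action plan and give it to the participant". Arm 1 receives a flyer on the same topic, and both arms receive the text message.

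The endpoint survey also covers implementation, "with a specific focus on whether the interventions elicited responses along the intended pathways and assess subjective rating or satisfaction of interventions by participants" (section 7.2.2.1). These items are to be assessed as in Aim 2, where one example in section 7.2.1.1 is "did CHW counseling improve trust and perceptions of RSV susceptibility".

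On masking, section 9.3.2 says only: "The study statistician will be blinded to treatment arm".

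**The concern.** Arm 2 is taught a behavior, commits to it in writing, and is then asked by study staff, preferably face to face, whether it was done for each named person. A counseled participant has more reason than a flyer recipient to answer yes. A collector who knows or learns the arm can add to that. Both effects favor Arm 2.

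Masking the statistician does not touch this, because the error is already in the data. Nor can later analysis separate true discussion from coached reporting, since no corroborating source is planned. At stake is what a positive Activate result means: more conversations, more reported conversations, or a mixture.

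**Working it through.** **Inputs.** From section 9.3.1: SD 0.3 for the per-participant proportion, 175 per arm, 10% attrition (0.90 × 175 = 157.5, taken as 157), alpha 0.05, target difference 10 points with 30% against 40% as the example. Sidedness is not stated, so two-sided is assumed. The net reporting bias *b* (over-reporting in Arm 2 minus that in Arm 1) is an assumption.

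**The protocol's own figure.** The standard error of the difference is 0.3 × √(2/n):
- n = 175: 0.3 × √(2/175) = 0.0321
- n = 157: 0.3 × √(2/157) = 0.0339, or 3.4 points

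Power for 10 points is Φ(0.10/SE − 1.96), which is 87.7% at 175 per arm and 84.0% at 157. The stated 80% is conservative; nothing below depends on it.

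**Rejection with no true effect.** If reporting shifts the Arm 2 mean by *b* and leaves the SD unchanged, the chance of a significant result is P(|Z + b/SE| > 1.96). For b = 0.03 at 157 per arm, b/SE = 0.03/0.0339 = 0.89 and the probability is 14.4%.

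| Assumed net bias | 157 per arm | 175 per arm |
|---|---|---|
| 0 | 5.0% | 5.0% |
| 2 points | 9.1% | 9.6% |
| 3 points | 14.4% | 15.5% |
| 5 points | 31.5% | 34.4% |

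**The same in terms of contacts.** Suppose 30% of contacts are truly spoken to in both arms, the lower value in the protocol's example. Then 70% are not, and an excess false-yes rate *f* in Arm 2 among those contacts gives b = 0.70 × f.
- 3 points: f = 0.03/0.70 = 4.3%
- 5 points: f = 0.05/0.70 = 7.1%
- The significance threshold at 157 per arm is 1.96 × 0.0339 = 6.6 points, so f is about 9.5%
- The full 10-point target: f = 0.10/0.70 = 14.3%

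The documents give no value for *f* or *b*. The figures show how sensitive the comparison is, not how much over-reporting to expect.

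**The case against.** The best reply is that much of this rests on silence. A reader might infer that interviewers know the arm, or that counselors collect the endpoint. The protocol says neither, and section 5.2.1 gives enrollment to university study staff rather than to the community health workers. A reader might also infer that the arm-revealing items come before the outcome items. No order is fixed, and section 7.2.2.1 describes the contact-by-contact questions first. The explicit counseling item is an example from the Aim 2 survey that reaches Aim 3 by cross-reference. Item order and field access often sit in data-collection forms, which are not shown.

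There are real safeguards too. Arm 1 gets same-topic material, so only excess over-reporting in Arm 2 matters. The denominator is fixed by the baseline list. Each contact is asked about separately, with reasons and the outcome of the conversation, and a participant who says no is offered a question about plans to discuss. Section 4.3.4 allows remote REDCap completion in Aim 2, and section 7.3 says that the two trials share a schedule of assessments and procedures, so self-entry may already be open to Aim 3.

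These points limit the claim but do not remove it. A fixed denominator does not protect the numerator, and follow-up questions may deter false answers but verify none. The Aim 3 text names only in-person, phone and Zoom follow-up, with a stated preference for in person. Who collects a self-reported primary outcome, by what mode and with what masking is trial conduct that the protocol has partly fixed.

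**Conclusion.** The concern holds as a risk of bias in the Activate primary comparison. The outcome is uncorroborated self-report, collected live with face-to-face preferred; one arm is coached in the behavior asked about; and no masking is stated at the point of collection. An assumed net bias of 3 points raises two-sided rejection under no effect to about 14%, and 5 points, half the target effect, to about 31%. These figures rest on SD 0.3, about 157 per arm, a two-sided 5% test and a simple shift in the Arm 2 mean.

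The documents do not support going further and saying that interviewers are unmasked by design, that the survey order primes the answer, or that a positive result would be an artifact. Participants know whether they were counseled, so no collection procedure can remove the problem entirely.

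**What to change.** In section 7.2.2.1, with a matching statement on masking in section 9.3.2:
1. Have existing university study staff who did not deliver counseling and cannot see the arm field collect the Aim 3 endpoint.
2. Have the contact-by-contact module completed and locked before any satisfaction, pathway or counseling item appears.
3. Make participant self-entry on a device or REDCap link the default, with staff help for literacy, in place of the preference for in-person administration.
4. Use the same item order for the self-reported Aim 2 secondary outcomes.
5. Describe a positive Activate result as an effect on self-reported discussion.

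The cost is form ordering and an access setting, with existing staff and software; endpoint, sample size and visits are unchanged. Some participants will need help, since the protocol provides for those who cannot read, and self-entry may leave some items missing, so completion should be monitored. The change must be in place before endpoint collection because it cannot be made good afterwards.
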